3.2 Number of subjects

Fifty (50) evaluable subjects (visit 2 performed successfully) will be recruited at five international clinics in order to meet the requirement for recruitment in the investigation. The number of subjects to be included for each centre will be approximately 10. The sponsor will be able to control the inclusion by distribution of devices to each centre.

CBAS5539 CIP Version 5

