10.4 General statistical methodology

All statistical analyses will be paired non-parametric. In order to choose the most powerful test, the Fisher's non-parametric permutation test for paired observations will be used for all paired analyses of continuous variables. For paired analysis of dichotomous and ordered categorical variables the Sign test will be used.

The main efficacy analysis will be performed on the ITT population and complementary efficacy analyses will be performed on the PP population. The main analysis will be performed after the 3 month visit. A complementary analysis will be performed 9 months after the main analysis (12-month visit). All significance tests will be one-sided and performed at the 5% significance level.

Imputation of missing values (definitions made in SAP) will be performed for all efficacy variables. No imputation of baseline values or baseline carry forward will be made.

All analyses, tables and figures will be produced for SSD and Conductive/Mixed separately and also pooled as on population.

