1.5.3 Overall sample size considerations

In order to achieve 90% power both for the primary analysis (PTA4 and SNR, Investigational Device vs. unaided) and the primary safety analysis, 50 evaluable subjects are needed. Each arm SSD and Conductive/Mixed should at least consist of 13 patients to assure a power of 90% in both arms for the primary analyses.

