If the first analysis is significant the probability mass 0.025 will go to the second analysis. If the second analysis is also significant the probability mass 0.025 will go to the third analysis and so on. When the first non-significant analysis is reached this and all analyses thereafter will be non-confirmative while the previous analyses will be confirmative. If the first analysis is non-significant no analysis will be confirmative.

STATISTISKA KONSULTGRUPPEN		Statistical Analysis Plan	
Protocol: Clinical performance of a new implant system for bone conduction hearing		Protocol No: CBAS5539	
		Version: 1.0	Page 14 of 22

The hierarchical testing will be made for each arm separately (SSD and Mixed/Conductive) and not totally.

We plan to analyse the similarity of the primary efficacy results among sites using non-parametric one way analyses of variance (Kruskal-Wallis test) of the difference between Unaided and ATB at 3 months. This will only be made totally and not by SSD and Mixed conductive.

Imputation of missing values will be performed for all efficacy variables. No imputation of baseline values or baseline carry forward will be made. Imputations will be made according to the following rules:

1. If a value is missing at the end of a patient, last observation will be carried forward.
2. If a missing value is occurring between two time points with values, an interpolation will be made for continuous variables and for categorical variables the value from the previous visit will be carried forward.

The distribution of continuous variables as well as change in continuous variables will be given as n, mean, SD, SEM, Median, Min and Max and the distribution of dichotomous and categorical variables will be given as number and percentages. One sided 97.5% CI will be presented where applicable.

Numbness, Adverse Events, Device deficiencies, Comfort, Usage, Surgical variables, Demographics, Baseline, Questions, Magnet strength variables will only be analysed descriptively.

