4.10 Efficacy Analyses

4.10.1 Primary Efficacy Analysis

Primary efficacy analysis will be determined by analysis of change in free-field threshold audiometry: PTA4 (mean of 500, 1000, 2000 and 4000Hz) and change in Adaptive speech recognition in noise (50% performance), from unaided versus Investigational device at the 3 months visit for the ITT population, using Fisher’s one-sided non-parametric permutation test for paired observations at a significance level of 0.025 to demonstrate an improvement in PTA4. Each arm SSD and Conductive/Mixed will be tested separately. Both PTA4 and SIQ must be significant at alpha 0.025 for the primary analysis to be considered as confirmative in each arm separately. In addition, a pooled analysis for all subjects will be made.

Group mean free-field PTA4 (average of 500, 1000, 2000, and 4000 Hz) with the Osia System at the 3-month postoperative interval will be improved over that measured preoperatively in the unaided condition (baseline).

This endpoint is represented by the following hypotheses:

$$H_0: \mu_F - \alpha_0 \geq 0,$$

$$H_a: \mu_F - \alpha_0 < 0,$$

where:

α_0 = baseline preoperative PTA4;

μ_F = mean follow-up PTA4 3 months postoperative.

Group mean Adaptive speech recognition in noise (50% performance), speech to noise ratio (SNR) with the Osia System at the 3-month postoperative interval will be improved over that measured preoperatively in the unaided condition.

Protocol:

Clinical performance of a new implant system for bone conduction hearing

Protocol No:

CBAS5539

Version:

1.0

Page 16 of

22

This endpoint is represented by the following hypotheses:

$$H_0: \mu_F - \alpha_0 \geq 0,$$

$$H_a: \mu_F - \alpha_0 < 0,$$

where:

α_0 = baseline preoperative Adaptive speech recognition in noise (50% performance), speech to noise ratio (SNR);

μ_F = mean follow-up Adaptive speech recognition in noise (50% performance), speech to noise ratio (SNR) 3 months postoperative.

A sensitivity analysis of the primary variable will be done for complete cases.

The primary analyses will be performed regardless of what Osia Fitting Software version (1.0.2 OFS or 1.0.3 OFS) used at 3 months (see chapter 4.12).

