6 CHANGES OF ANALYSIS FROM PROTOCOL

No changes of the analyses according to the protocol are made.

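### The site-similarity test pools SSD and Conductive/Mixed subjects without stratifying by arm, so if the arms' mean changes differ its result depends on each site's case mix

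*SAP*

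**What the plan says.** SAP 4.1 plans to examine site similarity of the primary efficacy results by "non-parametric one way analyses of variance (Kruskal-Wallis test) of the difference between Unaided and ATB at 3 months", and adds: "This will only be made totally and not by SSD and Mixed conductive". No level is given for this test and no action is attached to its result.

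Elsewhere the two hearing-loss groups are kept apart. SAP 4.10.1 says of the primary analysis: "Each arm SSD and Conductive/Mixed will be tested separately". The testing hierarchy in SAP 4.1 is likewise run within each arm. Protocol 10.4 sets a general rule: "All analyses, tables and figures will be produced for SSD and Conductive/Mixed separately and also pooled as on population". SAP section 6 states: "No changes of the analyses according to the protocol are made".

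On numbers, Protocol 3.2 says that 50 evaluable subjects "will be recruited at five international clinics", and "The number of subjects to be included for each centre will be approximately 10". The only arm quota is overall: "Each arm SSD and Conductive/Mixed should at least consist of 13 patients" (SAP 1.5.3). Arm is fixed by diagnosis, and Protocol 3.5 rules out randomisation.

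**The concern.** The site check does not match what it checks. The primary results are two sets of arm-specific changes; the check compares sites on one mixed set. If SSD and Conductive/Mixed subjects change by different amounts on average, a site's mean change depends on its share of SSD subjects. Sites with different shares can then look dissimilar although they perform identically. If the shares are equal, the between-arm variation sits inside every site and masks a site that truly differs.

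At stake is the only between-site comparison that the plan specifies. It could send readers after a site problem that is only case mix, or reassure them wrongly. There is also a documentary mismatch: the SAP excludes a by-arm version of this analysis, the protocol's general rule calls for one, and the SAP declares no changes.

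**Working it through.** **Inputs.** Five sites of about 10 (Protocol 3.2). SD of change 9.5 dB for PTA4 and 11.3 for SNR (SAP 1.5.1), both from Mixed/Conductive subjects only. Assumed, because the documents are silent: the gap *d* in mean change between arms (0, 5, 10, 15 dB), the same SD in both arms, normal changes, the SSD count per site, and a nominal 5% level.

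**The plan's own figure.** None exists for the site test. The nearest is the sample size of 11 (PTA4) and 13 (SNR) per arm. With n = (SD × (1.960 + 1.282)/10)²:
- PTA4: (9.5 × 0.3242)² = 9.5, so 10 (stated 11).
- SNR: (11.3 × 0.3242)² = 13.4, so 14 (stated 13).

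Both are within one subject of the stated figure, so the SDs are being read as intended: as SDs of the change. Noncentral t gives 12 and 16. The plan's figures came from simulation on data not in the documents, and nothing below depends on them.

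**Mechanism.** At a site with SSD share p, the expected mean change is (Conductive/Mixed mean) + p·d. At d = 10 dB:
- Shares 0.1 to 0.9: site means spread over 0.8 × 10 = 8 dB with no site effect.
- Shares 0.3 to 0.7: 0.4 × 10 = 4 dB.
- All shares 0.5: no spread, but the SD within a site rises to √(9.5² + 0.25 × 10²) = 10.7 dB, or √(9.5² + 0.25 × 15²) = 12.1 dB at d = 15. The test treats that balanced arm variation as noise between sites, so it becomes conservative.

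**Tests compared.** The pooled test is H = 12/(N(N+1)) · Σ R_j²/n_j − 3(N+1), with N = 50, against chi-square on 4 df. The stratified test ranks within arm and sums over arms: T_j = Σ_a [R_aj − n_aj(n_a+1)/2]/(n_a+1). The quadratic form T′V⁻¹T over four of the five sites is referred to the same chi-square. There were 20,000 simulated trials per setting (standard error at most 0.0035).

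**False rejection, no site effect, SD 9.5**

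| SSD per site | d = 0 | 5 | 10 | 15 dB |
|---|---|---|---|---|
| 1,3,5,7,9, pooled | 4.4% | 8% | 20% | 39% |
| 3,4,5,6,7, pooled | 4.5% | 4.4% | 3.9% | 3.1% |
| 5,5,5,5,5, pooled | 4.5% | 3.5% | 1.4% | 0.3% |
| Stratified, all mixes tried | 4.1–4.6% | 4.1–4.6% | 4.1–4.6% | 4.1–4.6% |

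Thirteen SSD subjects at only two sites (4 and 9) is more extreme: about 12%, 40% and 75% at 5, 10 and 15 dB. With SD 11.3 and mix 1,3,5,7,9 the pooled test gives 7%, 15% and 29% at the 5% level, and 3.5%, 8.5% and 18% at 2.5%.

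**Power, even mix, one site off by 10 dB.** Pooled: 54%, 49%, 36% and 18% at d = 0, 5, 10 and 15. Stratified: about 53% throughout.

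**Cost of stratifying when site and arm are entangled.** With 1,3,5,7,9 and an end site off by 10 dB, stratified power is about 44%, against 54% for the pooled test at zero gap. If the outlying site holds 9 of 13 SSD subjects, it is about 20%.

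**Separate tests by arm.** With 25 per arm (five per site) and one site off by 10 dB, power is about 21% in each arm. With 13 SSD subjects spread 3,3,3,2,2, the SSD-only test has about 2%.

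**The case against.** The strongest reply is that every harmful figure needs a gap between arms that the documents do not supply. Neither document says the arms are separated because their changes should differ; the sample-size sections apply the same 10 dB target and the same SDs to both. At zero gap the pooled test is valid and loses nothing. That stands, although the plan gives no basis for assuming zero either.

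Second, inflation needs marked clustering of diagnoses by site. Mild unevenness produces none, and if the mix varies between sites only by chance the rejection rate averages 4–4.5% at every gap tried, up to 20 dB. This also stands, with a limit: single realised mixes can be far from that average, reaching 60–69% in the worst cases at 20 dB.

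Third, testing pooled has a plausible motive. At the 13-subject minimum an arm has 13/5 = 2.6 subjects per site, too few for a by-arm test. That is a good argument against separate tests, but not against stratification.

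Fourth, Protocol 10.4 contains no site test; the SAP adds one, so the conflict is with a general sentence rather than a specified analysis. That is fair, but the sentence covers all analyses and SAP section 6 does not mention an exception.

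A reader might go further and infer that the efficacy conclusions are compromised, or that the site test will mislead. The documents support neither. The confirmatory tests are paired within subject and run by arm, site does not enter them, the site test is outside the hierarchy, and the actual mix per site is not given.

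**Conclusion.** The point holds as a limited design weakness in a supportive analysis. An unstratified site test is the wrong match for arm-specific results when nothing balances the arms within sites. How much this matters depends on two unknowns: the gap between arms and how unevenly SSD subjects are spread. Under the assumed 5–15 dB gaps, the consequences run from negligible (mild unevenness at 5 dB) to roughly four to eight times the nominal false-positive rate at 10–15 dB with strong clustering (20/5 = 4; 39/5 = 7.8). With an even mix the loss is in power: a third at 10 dB (54% to 36%) and two thirds at 15 dB (54% to 18%). At zero gap there is no fault in the test, and the primary results are unaffected in every case. The mismatch between SAP 4.1, Protocol 10.4 and SAP section 6 does not depend on these assumptions.

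**What to change.** Replace the pooled Kruskal-Wallis test in SAP 4.1 with one arm-stratified site test (ranks within arm, van Elteren-type combination) for both PTA4 and SNR, and state its level. Add a descriptive table of the 3-month change by site and arm, with counts, so that any clustering is visible. Replace the whole sentence that confines the test to the pooled population; striking only the reference to the two arms would leave a pooled-only test. Then reconcile SAP 4.1 with Protocol 10.4, and record in SAP section 6 any part of the by-arm rule that is not followed.

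The cost is a few SAP sentences and one table. No new data are needed and the primary tests do not change. Under an even mix the stratified test gives up about one percentage point of power at zero gap. Under strong entanglement it is weaker than the pooled test is at zero gap (about 44% or 20%, as above), because the data cannot then separate site from arm; the report should say so if the table shows it. Two alternatives are worse. Separate tests by arm have too little power. Subtracting arm medians before a pooled test can absorb a real site effect when one site supplies most of an arm: power is about 10%, against 20% for ranking within arm.

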9.3 Risks associated with participation in the clinical investigation

The Investigational device is reused by several parts from already CE marked products. There is no guarantee that the ATB Implant will not cause any adverse device events. The ATB Implant is expected to have a lifetime of about ten years. By the time of first implantation in the clinical investigation, spring 2017, it will be possible to claim approximately 30 months of equivalent lifetime. Test results will be reported periodically until an equivalent lifetime of 10 years is reached. As with any new surgical product and medical device, there is a risk that unanticipated Adverse Events may occur. The subjects will be closely monitored in the investigation and instructed to contact the responsible investigator if they experience any untoward effect. In the worst case scenario the patient would need a revision surgery to remove the ATB Implant, but this can be done with local anaesthesia. They will then end participation in the clinical investigation and follow normal clinical care and follow up.

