3.2.2 Secondary Efficacy Variables/endpoints

- Abbreviated Profile of Hearing Aid Benefit (APHAB) at visit 1 (unaided), m 3, m 6 and m 12:
 - Global score
 - Ease of Communication
 - Reverberation
 - Background Noise
 - Aversiveness
- Thresholds audiometry: PTA-4, 250, 500, 1000, 2000, 3000, 4000, and 6000 Hz at visit 1, w 4, m 3, m 6 and m 12
- Speech perception in quiet (50dB, 65dB and 80dB SPL) at visit 1, w 4, m 3, m 6 and m 12
- Adaptive speech recognition in noise (50% performance) at visit 1, w 4, m 3, m 6 and m 12
- Feedback measurement at each frequency at visit w 4, w 6, m 3, m 6 and m 12
- Generic quality of life scale: Health Utility Index (HUI) at visit 1 (unaided), m 3, m 6 and m 12:
 - Health related quality of life score for overall health
 - Vision score
 - Hearing score
 - Speech score
 - Ambulation/mobility score
 - Dexterity score
 - Self-care score
 - Emotion score
 - Cognition score
- The Speech, Spatial and Qualities of Hearing Scale (SSQ) at visit 1 (unaided), m 3, m 6 and m 12

Surgical variables

- Soft tissue thickness (mm)
- Surgery time (time of first incision to time of last suture), (min)

Protocol:

Clinical performance of a new implant system for bone conduction hearing

Protocol No:

CBAS5539

Version:

1.0

Page 12 of
22

- Type of anaesthesia
- Soft tissue thinning performed
 - Yes
 - No
- Bone polishing/removal below the actuator site performed
- BI300 length
 - 3 mm
 - 4 mm
- Location of BI300 Implant
- Surgical incision/location

Questions about usage will be collected at w 6, w 12, m 6 and m 12:

- Daily use of sound processor (hours/day)
- Softpad use
- Question about comfort with the SP, using VAS, will be collected at w 4, w 6, m 3, m 6 and m 12.
- Magnet choice will be recorded at w 4, w 6, w 12, m 6 and m 12.

BC Direct thresholds at visit 1, w 4, w 6, m 3, m 6 and m 12

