7 LISTING OF TABLE, FIGURES AND LISTINGS

7.1 Listing of Tables

Table 14.1.1	Patient Disposition and Data Sets Analysed
Table 14.1.2	Protocol Deviations Leading to Exclusion from PP Population (ITT Population)
Table 14.1.3.1	Demographics and Baseline Characteristics (ITT Population)
Table 14.1.3.2	Demographics and Baseline Characteristics (PP Population)
Table 14.1.4.1	Pre operation (ITT Population)
Table 14.1.4.2	Pre operation (PP Population)
Table 14.1.5.1	Audiogram (air) at visit 1, 6 and 8 - SSD patients (Safety Population)
Table 14.1.5.2	Audiogram (bone) at visit 1, 6 and 8 - SSD patients (Safety Population)
Table 14.1.5.3	Audiogram (air) at visit 1, 6 and 8 - conductive patients (Safety Population)
Table 14.1.5.4	Audiogram (bone) at visit 1, 6 and 8 - conductive patients (Safety Population)
Table 14.1.6	Medical History (ITT Population)
Table 14.1.7	Surgical History (ITT Population)
Table 14.1.8.1	Prior Medications (ITT population)
Table 14.1.8.2	Concomitant Medications (ITT population)
Table 14.1.9	Listing of Concomitant Treatments/Procedures (ITT population)
Table 14.2.1.1	Threshold Audiometry - Free field ATB System vs Unaided (ITT Population)
Table 14.2.1.2	Threshold Audiometry - Free field ATB System vs Unaided (PP Population)
Table 14.2.2.1	Adaptive speech recognition in noise and Speech in quiet ATB System vs Unaided (ITT Population)
Table 14.2.2.2	Adaptive speech recognition in noise and Speech in quiet ATB vs Unaided (PP Population)
Table 14.2.3.1	BC Direct (ITT Population)
Table 14.2.3.2	BC Direct (PP Population)
Table 14.2.4.1	HUI (ITT Population)
Table 14.2.4.2	HUI (PP Population)
Table 14.2.5.1	APHAB (ITT Population)
Table 14.2.5.2	APHAB (PP Population)
Table 14.2.6.1	The Speech, Spatial and Qualities of Hearing Scale (SSQ) (ITT Population)
Table 14.2.6.2	The Speech, Spatial and Qualities of Hearing Scale (SSQ) (PP Population)
Table 14.2.7.1	Surgery (ITT population)
Table 14.2.7.2	Surgery (PP population)
Table 14.2.8.1	Magnet strength (ITT population)
Table 14.2.8.2	Magnet strength (PP population)
Table 14.2.9.1	Daily use and soft-pad use (ITT population)

Protocol: Clinical performance of a new implant system for bone conduction hearing	Protocol No: CBAS5539	
	Version: 1.0	Page 21 of 22

- Table 14.2.9.2 Daily use and soft-pad use (PP population)
- Table 14.2.10.1 Threshold Audiometry - Free field ATB System vs Unaided (SSD patients ITT Population)

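### Read literally, the SAP's carry-forward rule gives explanted subjects positive hours of use and a magnet in the later-visit ITT tables

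*SAP*

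**What the plan says.** SAP 4.1 sets the scope of imputation: "Imputation of missing values will be performed for all efficacy variables". For values missing after a subject's last visit the rule is: "If a value is missing at the end of a patient, last observation will be carried forward". The only stated limit concerns baseline: "No imputation of baseline values or baseline carry forward will be made". Nothing in the rule depends on why the value is missing.

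The SAP section headed "3.2.2 Secondary Efficacy Variables/endpoints" lists hours of daily use, softpad use, comfort on a visual analogue scale, and magnet choice. On timing it says: "Questions about usage will be collected at w 6, w 12, m 6 and m 12". Protocol 10.2.2 also lists all four under its efficacy heading.

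SAP 2.1.1 defines ITT as every operated subject. In SAP 7.1, Table 14.2.8.1 (magnet strength) and Table 14.2.9.1 (daily use and softpad use) are both on ITT. SAP 4.10.2 adds a flow graph of magnet changes.

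Protocol 9.3 says of subjects whose implant is removed: "They will then end participation in the clinical investigation and follow normal clinical care and follow up". Protocol 3.6 names implant loss as a reason for discontinuation, and protocol 3.7 does not replace subjects who discontinue after surgery.

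**The concern.** Carry-forward is normally a guess at a value that exists but was not observed. After explantation the hours of use are known to be zero and no magnet is worn. A positive number entered for that subject is therefore a false value, not an uncertain estimate. The usage question also has a fixed recall period (protocol 6.8: the week before Visit 5, the month before Visits 6 to 8), so an answer given at 3 months cannot describe month 12.

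Collecting information on magnet choice and daily use is a secondary objective (protocol 4.3), and protocol 4.2 justifies the length of follow-up by the need for long-term data. These variables are only described, so the tables are the whole result. If the denominator includes people without a device, the 12-month tables overstate use.

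**Working it through.** No figure in the plan is at issue, so the check follows the text and then illustrates the size.

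**Text**

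1. Scope: all efficacy variables (SAP 4.1).
2. Membership: daily use, softpad use, comfort and magnet choice are efficacy variables (SAP 3.2.2; protocol 10.2.2).
3. Trigger: an explanted subject ends participation (protocol 9.3), so every later visit is missing at the end of that subject's record.
4. Action: the last value is carried forward, with no condition on the reason.
5. Display: the subject stays in ITT (SAP 2.1.1) and so in Tables 14.2.8.1 and 14.2.9.1. No separate comfort table is listed, but SAP 4.1 calls for by-visit distributions of all efficacy variables where applicable.
6. Exemption: none found. SAP 4.1 says comfort, usage and magnet strength are analysed only descriptively. That rules out testing; it does not mention imputation. The complete-case sensitivity analysis in SAP 4.10.1 covers the primary variable only.

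**Boundaries**

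- A subject lost before the first record (week 6 for hours, week 4 for magnet) has nothing to carry.
- A last value of 0 h is carried as 0 h, which does no harm.
- Only safety is evaluated at the 6-month lock (SAP 4.2), so imputed month-6 and month-12 use would both appear at the 12-month lock. A subject explanted between week 6 and month 3 could also affect the 3-month tables.

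**Size**

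Inputs: N = 50 (protocol 3.2). The number of explants k and the last reported hours H are not in the documents. H = 6 to 10 h/day is an assumption.

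Overstatement of the mean, compared with coding explants as 0 h: k × H / N.

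| k | H = 6 | H = 10 | Subjects with a device |
|---|---|---|---|
| 1 | 1 × 6 / 50 = 0.12 h | 1 × 10 / 50 = 0.20 h | 49/50 = 98% |
| 2 | 2 × 6 / 50 = 0.24 h | 2 × 10 / 50 = 0.40 h | 48/50 = 96% |

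Under the rule, all 50 would count as users. Each explanted subject therefore adds 1/50 = 2 percentage points to the share using the device.

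The only implant-loss figures in the protocol are for predecessor systems: around 1% for Baha Connect (9.2.4) and no confirmed loss from osseointegration failure for Baha Attract (9.2.5). At 1%, 50 × 0.01 = 0.5 subjects would be expected. Explantation for other reasons is not covered by those figures. One explant is a reasonable illustration; larger numbers have no support in the documents.

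**The case against.** **The intended scope may be narrower.** SAP 4.1 groups comfort, usage and magnet strength with adverse events and demographics as descriptive. Daily use, softpad use and comfort do not appear among the analyses in SAP 4.10.2 or protocol 10.5.2. The heading of SAP 3.2.2 also covers one-off surgical items, for which carry-forward has no meaning. The authors may never have meant to impute hours of use. That is a fair doubt about intent, but the written rule says all efficacy variables, and a programmer following it would impute these too.

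**Stopping is reported elsewhere.** A reader might infer that the rule hides stopping from the report. It does not. SAP 4.3 presents premature withdrawals with reasons. The adverse events of special interest include events that interfere with daily use and those leading to explantation (SAP 3.3.2), and they are summarised under SAP 4.11.2. Per-protocol use and magnet tables (14.2.8.2 and 14.2.9.2) should drop subjects who did not complete. All of this stands, but none of it corrects the ITT use and magnet tables.

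**Withdrawal is not explantation.** A reader might extend the point to everyone who leaves. A subject who withdraws with the implant in place may still wear the processor, so only the explanted subject's value is known to be wrong.

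**Comfort could move either way.** A reader might infer that carry-forward inflates comfort. If a subject leaves because the device is uncomfortable, carrying the last score keeps a poor value in the mean, and observed-case reporting would remove it. The documents do not establish a direction.

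**The consequence is small.** These variables are outside the testing hierarchy and support no confirmatory claim. This stands, and it limits the severity.

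**Conclusion.** The rule is wrong as written, at minor severity. Taken literally, it places a subject with no device in the ITT use and magnet tables with positive hours and a magnet. For subjects who discontinue with the implant in place, it presents an unverified value as data.

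The conclusion about explanted subjects rests on the wording alone. The size rests on an assumed 6 to 10 h/day as the last report: 0.12 to 0.20 h/day and 2 percentage points per explanted subject at N = 50. Someone about to lose or give up the device may have been using it less, and the effect would then be smaller.

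A larger distortion, from several explants falling in one arm, might be inferred, but it needs counts that the documents do not give. SAP 7.1 also lists no daily-use table by arm, although protocol 10.4 asks for all tables by arm. Primary and hierarchical results are unaffected.

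**What to change.** In SAP 4.1, exempt daily use, softpad use, comfort and magnet choice from imputation, and report observed n at each visit.

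In Tables 14.2.8.1 and 14.2.9.1 and in the magnet flow graph:

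- show subjects known to be explanted as non-users from that point: 0 h/day in the use table, and a separate explanted state for magnet;
- show other discontinued subjects as discontinued, use unknown;
- add a row for n (%) using the device at each visit, with all operated subjects as the denominator.

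The cost is a few lines of SAP text and a small change to two tables and one graph. No new data are needed: protocol 12.4 already requires the explant date, and discontinuation is recorded. For withdrawals with the implant in place, use after withdrawal is not collected, which is why they need the unknown category rather than a zero.

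There are two consequences to accept. Reported use may look slightly less favourable. Observed-case comfort should be read beside the number discontinued, because losing poor last scores could raise the mean.

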3.6 Discontinuation

- Subjects are free to discontinue their participation in the investigation at any time
- Subjects may be discontinued from the investigation at any time at the discretion of the investigator
- Other reason for subject withdrawal or discontinuation, e.g. implant loss

Subjects who themselves discontinue from the investigation should always be asked about the reason(s) for the discontinuation and the presence of any adverse events. If possible, the subject should always be seen and assessed by an investigator. Any adverse event should be followed up.

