2 STUDY POPULATIONS

2.1 Definition of Study Populations

The final definition of the analysis sets (ITT, PP and Safety) will be taken at the clean file meeting before database lock.

Protocol:

Clinical performance of a new implant system for bone conduction hearing

Protocol No:

CBAS5539

Version:

1.0

Page 10 of

22

2.1.1 *Intent-to-Treat Population (Full Analysis Set)*

The Intention-to-Treat population (ITT) will include all subjects who have undergone surgical intervention.

2.1.2 *Per-Protocol Population*

The Per Protocol population (PP) will include subjects that have completed the investigation according to the protocol. Subjects that were incorrectly included or were considered major protocol violators should be removed from the PP population.

2.1.3 *Safety Population*

The Safety population consists of all surgically treated subjects

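### Does the plan need an extra analysis of PTA4 and SNR in which a lost implant counts as no benefit?

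*SAP*

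**What the plan says.** **Imputation.** SAP 4.1 imputes all efficacy variables after baseline. Its end-of-follow-up rule is "If a value is missing at the end of a patient, last observation will be carried forward", and gaps between visits are interpolated for continuous variables. It also states "No imputation of baseline values or baseline carry forward will be made", and protocol 10.4 says the same.

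**Implant loss.** Protocol 3.6 lists "Other reason for subject withdrawal or discontinuation, e.g. implant loss". Protocol 9.3 says of subjects whose implant is removed: "They will then end participation in the clinical investigation and follow normal clinical care and follow up". Protocol 3.7 allows no replacement after surgery.

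**Measurements.** Aided free-field thresholds and speech in noise are taken at Visits 4, 6, 7 and 8 (protocol 6.2 and 6.4), not at Visit 5.

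**Populations.** SAP 2.1.1: "The Intention-to-Treat population (ITT) will include all subjects who have undergone surgical intervention". The per-protocol set consists of subjects who completed according to protocol, and SAP 2.1 adds "The final definition of the analysis sets (ITT, PP and Safety) will be taken at the clean file meeting before database lock".

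**Analyses.** SAP 4.10.1 tests PTA4 and SNR at 3 months in each arm with a one-sided paired permutation test at 0.025, and plans a complete-case sensitivity analysis. SAP 4.1 reports n, mean, SD, SEM, median, minimum and maximum of change, and adds "One sided 97.5% CI will be presented where applicable". Protocol 10.4 requires all analyses and tables for SSD and Conductive/Mixed separately as well as pooled. SAP 6 states "No changes of the analyses according to the protocol are made".

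**The concern.** For an implanted device analysed in all operated subjects, a reader expects a lost implant to count against the device. Here it does not. A loss between Visit 4 and Visit 6 contributes the 4-week aided value to the 3-month result. A loss before Visit 4 contributes nothing, because there is no aided value to carry and the baseline may not be used. Complete cases leave both kinds out, and the per-protocol set probably does too.

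If the working device helps, the reported mean and confidence limit would then describe subjects who keep a working device. They would look somewhat better than the result for everyone implanted. An obvious remedy would be a second sensitivity analysis with change set to zero for these subjects.

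**Working it through.** **1. Inputs.** SD of paired change 9.5 dB (PTA4) and 11.3 (SNR), target difference 10 on both, one-sided alpha 0.025 and at least 13 subjects per arm (SAP 1.5.1 and 1.5.3). An arm of 25 is half of the 50 planned subjects. Implant loss is around 1% for Baha Connect, with no period stated (protocol 9.2.4). No osseointegration loss is confirmed for Baha Attract (protocol 9.2.5), and protocol 9.1 expects the ATB risk to be similar to that system's.

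**2. The plan's own figures.** The paired normal approximation is n = (SD × (1.960 + 1.282) / 10)².
- PTA4: 9.48, so 10; the plan says 11.
- SNR: 13.42, so 14; the plan says 13.

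Both are close. The plan simulated from earlier study data that are not in the documents, so exact agreement is not expected. The SDs can be used as SDs of paired change.

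**3. The test.** The paired permutation test flips the sign of each difference. A difference of zero is the same under either sign, so adding zeros changes neither the observed sum nor its permutation distribution. Full enumeration of the sign flips for 80 simulated data sets (12 values against the same 12 plus one zero) gave a largest p-value difference of 0. If the missing 3-month values are implant losses, the planned complete-case p-value is therefore the zero-change p-value.

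**4. The estimate and limit.** Let the complete cases be n − k values with mean m and SD s, and let k subjects be lost. Adding k zeros gives

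M = (n − k) m / n

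V = [(n − k − 1) s² + (n − k) m² − n M²] / (n − 1)

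lower limit = M − t(0.975, n − 1) × √(V / n).

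Everything needed is n, mean and SD, which SAP 4.1 plans, plus the number of losses. In 200,000 simulated arms per case the limit from these formulas agreed with direct calculation to within 1e-14.

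Example, PTA4, n = 13, k = 1, m = 10, s = 9.5:
- M = 12 × 10 / 13 = 9.23
- V = (11 × 90.25 + 12 × 100 − 13 × 9.2308²) / 12 = 90.42, so SD = 9.51
- limit = 9.23 − 2.179 × 9.51 / √13 = 3.48

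**5. Size for one loss.** The table assumes a mean improvement of 10 and, for last observation carried forward (LOCF), that the carried value leaves mean and SD unchanged.

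| Endpoint, arm size | Shift of mean, 10/n | Limit, LOCF | Limit, complete case | Limit, zero change |
|---|---|---|---|---|
| PTA4, 13 | 0.77 | 4.26 | 3.96 | 3.48 |
| PTA4, 25 | 0.40 | 6.08 | 5.99 | 5.67 |
| SNR, 13 | 0.77 | 3.17 | 2.82 | 2.48 |
| SNR, 25 | 0.40 | 5.34 | 5.23 | 4.96 |

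Averaging over simulated arms instead of plugging in the means raises these limits by less than 0.2. If only half the benefit is present at week 4, the LOCF-to-zero shift of the mean is 5/n: 0.38 or 0.20. With three losses in an arm of 13, the zero-change limits are 2.06 (PTA4) and 1.21 (SNR), still above zero.

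**6. Likelihood.** At 1%, the expected shift of the mean is 0.01 × 10 = 0.10 dB. The chance of at least one loss is 1 − 0.99^13 = 12%, 1 − 0.99^25 = 22% and 1 − 0.99^50 = 39%.

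**The case for a change.** The strongest reply is that the reader should not have to do this arithmetic, and that the counts may not be printed. SAP 4.3 breaks withdrawal reasons down by treatment group, while SAP 1.4 recognises only one device group. The table list in SAP 7.1 shows no separate complete-case table. The SAP also does not name its method for the confidence interval, and an interval obtained by inverting the permutation test could not be rebuilt from summary statistics. In 50 subjects, at least one loss is quite possible.

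Part of this stands. The reconstruction needs the complete-case summary, the losses per arm and a t-based limit. But the complete-case analysis is planned in SAP 4.10.1, and protocol 10.4 requires all tables by arm, so withdrawal reasons should be available per arm. Explantation is also an adverse event of special interest, counted by subject in SAP 4.11.2. A subject lost before fitting shows up as a gap between the ITT count and the reported n of change.

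Zero change is itself an assumption. Unaided hearing after surgery need not equal baseline, and protocol 6.1 and 7.2.4 monitor bone-conduction thresholds for shifts. Adding the analysis would also contradict an explicit choice made in both documents.

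**Conclusion.** The concern does not hold. The plan does treat implant loss as described, but no rule, figure or test is wrong. The hypotheses in protocol 10.2.1 and SAP 4.10.1 are about hearing with the Osia System, and a zero-change estimate answers a different question. Excluding baseline carry-forward is a deliberate choice, the same in both documents. Success is decided by the tests at 0.025, not by the confidence limit, and the planned complete-case test already gives the zero-change p-value when the missing values are implant losses. The corresponding mean and t-based limit follow from planned summaries and the loss count.

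What is left is a preference for one more supporting estimate. It would differ from the LOCF mean by at most about 0.77 dB per loss in the smallest arm, and by about 0.10 dB in expectation at the 1% rate. These sizes assume a 10 dB benefit, the SAP's SDs, a t-based limit and a loss rate borrowed from a related system. No change to the plan is needed.
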